#### 4.3 STUDY TREATMENT AND OTHER TREATMENTS RELEVANT TO THE STUDY DESIGN

The investigational medicinal product (IMP) for this study is ocrelizumab. Appendix 7 identifies all IMPs and auxiliary medicinal products for this study.

# 4.3.1 Ocrelizumab Formulation, Packaging, and Handling

Ocrelizumab will be supplied by the Sponsor as a sterile, clear to slightly opalescent and colorless to pale brown solution for IV infusion and contains no preservatives. The ocrelizumab drug is provided as a liquid in a single–use 15–mL type 1, glass vial fitted with a 20-mm fluoro–resin–laminated stopper and an aluminum seal with a flip–off plastic cap. Each single-use, 15–mL vial supplied by the Sponsor contains 300 mg (nominal) of ocrelizumab formulated with 30 mg/mL ocrelizumab in 20 mM sodium acetate at pH 5.3, with 106 mM trehalose dihydrate and 0.02% polysorbate 20. Each vial contains 300 mg ocrelizumab at a nominal fill volume of 10 mL.

Ocrelizumab drug product may contain fine translucent and/or reflective particles associated with enhanced opalescence. Do not use the solution if discolored or if the solution contains discrete foreign particulate matter.

The hospital units/pharmacy will receive study medication kits for each patient. One study medication kit contains one single-use liquid vial with 300 mg ocrelizumab.

Ocrelizumab vials are stable at 2°C–8°C (refrigerated storage) and must be stored refrigerated until use. Ocrelizumab should not be used beyond the expiration date stamped on the carton. Expiration dating may be extended during the trial; the Sponsor will provide documentation.

Ocrelizumab is a protein. It is therefore important to handle the drug gently and to avoid foaming during product handling, dosage preparation, and drug administration, as foaming may lead to denaturing of the protein. Ocrelizumab vials should not be frozen or shaken and should be protected from light during storage.

The study medication labels will be produced in accordance with the local requirements.

# 4.3.2 Study Treatment Dosage, Administration, and Compliance

Any overdose or incorrect administration of study drug should be noted on the Study Drug Administration eCRF. Adverse events associated with an overdose or incorrect administration of any of the study treatments should be recorded on the Adverse Event eCRF. Section 5.3.5.13 summarizes available safety data related to overdosing of ocrelizumab.

Guidelines for treatment interruption or discontinuation for patients who experience adverse events are provided in Section 4.6.2.

# 4.3.2.1 Ocrelizumab

The study drug infusions should always be administered in a hospital or clinic environment under close supervision of the investigator or a medically qualified staff member with immediate availability of full resuscitation facilities. Patients may be hospitalized for observation at the discretion of the investigator (in some countries, this is the standard procedure).

### Preparation of Infusion Bags

Ocrelizumab dose solutions for IV administration must be prepared/diluted under appropriate aseptic conditions, as the drug does not contain antimicrobial preservatives.

Ocrelizumab drug must be diluted into normal saline (0.9% sodium chloride) infusion bags prior to administration by IV infusion.

It is important not to use evacuated glass containers (to prepare the infusion solution), which require vented administration sets because this causes foaming as air bubbles pass through the solution.

The ocrelizumab infusion solution should be prepared on the day of infusion and used immediately to limit microbial growth in case of potential accidental contamination. If not used immediately, the prepared infusion solution can be stored for up to 24 hours at  $2^{\circ}C-8^{\circ}C$ . Because ocrelizumab solutions for infusion do not contain a preservative, the prepared infusion solution of ocrelizumab is physically and chemically stable for up to 24 hours at  $2^{\circ}C-8^{\circ}C$  and subsequently 8 hours at room temperature. The ocrelizumab infusion solution must be completely administered to the patient within 32 hours of preparation (not exceeding 24 hours at  $2^{\circ}C-8^{\circ}C$  and 8 hours at room temperature). In the event an IV infusion cannot be completed the same day, the remaining solution should be discarded.

To avoid an infusion reaction associated with the administration of a low-temperature solution, the bag must be brought to room temperature before infusion. To do this, place the bag at room temperature for approximately 1 hour.

Transportation of the dose solution must be at  $2^{\circ}C-8^{\circ}C$  to ensure stability of diluted ocrelizumab solution.

Specific instructions are provided separately in the Dose Preparation Guidelines and must be followed exactly.

## 4.3.2.2 Monitoring prior to and during Infusions

All patients should receive premedications before any infusion (for detailed information see Section 4.3.3).

# 12-Lead ECG

ECGs should be performed prior to any procedures, such as vital sign measurements and blood draws. Whenever possible, the same machine should be used for each patient. Lead placement should be as consistent as possible. To minimize variability, it is important that patients be in a resting position for at least 10 minutes prior to each ECG evaluation.

Prior to study drug infusion, recording of 12–lead ECG will be done within 45 minutes prior to the methylprednisolone infusion.

After study drug infusion, recording of 12–lead ECG will be done within 60 minutes after completion of the infusion.

Further details are provided in Section 4.5.11.

# Vital Signs

Prior to study drug infusion, vital signs (i.e., pulse rate, systolic and diastolic blood pressure, respiratory rate, and temperature) will be taken within 45 minutes prior to the methylprednisolone infusion in all patients. In addition, vital signs should be obtained prior to the study drug infusion.

During the infusions, vital signs will be assessed every 15 ( $\pm$ 5) minutes for the first hour, then every 30 ( $\pm$ 10) minutes until1 hour after the completion of the infusion.

Additional vital sign readings and/or 12–lead ECG recordings may be taken at the discretion of the investigator in the event of an IRR or if clinically indicated and should be recorded on the corresponding unscheduled eCRF.

# 4.3.2.3 Infusion Procedures

Ocrelizumab drug product is a clear to slightly opalescent and colorless to pale brown liquid. Ocrelizumab may contain fine translucent and/or reflective particles associated with enhanced opalescence. Do not use the solution if discolored or if the solution contains discrete foreign particulate matter.

Prior to the start of the infusion, please be sure that the content of the bag is at room temperature to avoid an infusion reaction due to the administration of the solution at low temperatures. To do this, place the bag at room temperature for approximately 1 hour.

The infusion solution must be administered using a polyvinyl chloride, polyethylene, polybutadiene, or polyetherurethane infusion set equipped with a 0.2 or 0.22  $\mu$ m (or less) polyethersulfone or polysulfone filter.

Ocrelizumab should be given as a slow IV infusion. It must not be administered as an IV push or bolus. Well-adjusted infusion pumps should be used to control the infusion rate, and the study drug should be infused through a dedicated line.

A physician should be available on site with immediate availability of full resuscitation facilities.

After completion of the infusion, the IV cannula should remain in situ for at least 1 hour in order to be able to administer drugs IV, if necessary, in the event of a delayed reaction. If no adverse events occur during this period, the IV cannula may be removed.

Physicians should alert caregivers (and patients) that IRRs can occur within 24 hours of infusion.

In the event an infusion cannot be completed the same day, the remaining liquid in the infusion bag must be discarded.

### Initial Dose (Dose 1) as Two Infusions of Half the Dose 14 Days Apart

The initial ocrelizumab dose must be administered as two separate IV infusions of 150 mg (Cohort 1, 300–mg regimen) or 300 mg (Cohort 2, 600–mg regimen), which are given 14 days apart (i.e., Day 1 and Day 15).

It is recommended that the first infusion of ocrelizumab (Day 1 of Dose 1) be scheduled in the morning to allow the patient to stay at the hospital (or infusion center) with medical supervision and monitoring as required, as long as possible (e.g., until 6 p.m. or 8 p.m. according to the hospital rules), with a minimum of 1 hour after completion of the infusion. Patients may be hospitalized for a 24–hour observation after completion of the infusion at the discretion of the treating investigator.

Note: Any adverse event that results in hospitalization or prolonged hospitalization has to be reported as a serious adverse event (see Section 5.3.5.12). If the reason for hospitalization is not associated with an adverse event (e.g., for patient supervision purposes), no serious adverse event will be reported (Section 5.3.5.12).

It is also recommended to administer the second infusion (Day 15 of Dose 1) in the morning, as patients should remain under observation for at least 1 hour after the completion of the infusion and up to 24 hours at the treating investigator's discretion.

#### Ocrelizumab—F. Hoffmann-La Roche Ltd 57/Protocol WA39085, Version 10

For each infusion (Day 1 and Day 15), it is necessary to prepare a single infusion bag (250 mL, 0.9% saline solution) containing either 150– or 300–mg ocrelizumab.

The infusion of ocrelizumab 150 or 300 mg should be initiated at a rate of 30 mL/hr. Thereafter, the rate can be increased in 30–mL/hr increments every 30 minutes to a maximum of 180 mL/hr.

Infusion of 150 and 300 mg of ocrelizumab should be given over approximately 2.5 hours.

Because of a possible need to vary infusion rates depending on tolerance of the infusion, patients and parents should be informed that the total infusion time may exceed the time stated.

Unless an infusion reaction occurs that necessitates discontinuation, the entire content of infusion bag must be administered to the patient.

Specific instructions will be provided separately in the Dose Preparation Guidelines and must be followed exactly.

#### Subsequent Doses in the Optional Ocrelizumab Extension

Subsequent doses will be administered only to patients continuing in the OOE period as a single infusion (e.g., 300 or 600 mg) of ocrelizumab every 24 weeks, if safety and tolerability in children and adolescents allow it, until the appropriate dose of ocrelizumab for the subsequent Phase III study in children and adolescents is selected by the IMC. At that time, patients will switch to this selected dosing regimen of ocrelizumab at their next infusion visit.

Patients in Cohort 1 who reach a stable body weight of  $\geq$  40 kg during the study will be automatically switched to the appropriate dose for patients with body weight  $\geq$  40 kg (see Section 3.1.1).

In a situation where the subsequent dose is higher than the dose in the initial treatment regimen, that subsequent dose will be administered as two infusions of half the dose 14 days apart to mitigate the risk and severity of IRRs.

It is recommended that subsequent infusions be administered in the morning, as patients should remain under observation for at least 1 hour after the completion of the infusion and up to 24 hours at the treating investigator's discretion.

Infusion of ocrelizumab 300 mg (250–mL infusion bag, 0.9% saline solution) should be initiated at a rate of 30 mL/hr. Thereafter, the rate can be increased in 30-mL/hr increments every 30 minutes to a maximum of 180 mL/hr. Infusion of 300 mg of ocrelizumab should be given over approximately 2.5 hours.

Infusion of ocrelizumab 600 mg (500–mL infusion bag, 0.9% saline solution) should begin at a rate of 40 mL/hr. Thereafter, the rate can be increased in 40-mL/hr increments every 30 minutes to a maximum of 200 mL/hr. Infusion of 600 mg of ocrelizumab should be given over approximately 3.5 hours.

Because of a possible need to vary infusion rates depending on tolerance of the infusion, patients, and parents should be informed that the total infusion time may exceed the time stated.

Unless an infusion reaction occurs that necessitates discontinuation, the entire content of infusion bag must be administered to the patient.

Specific instructions will be provided separately in the Dose Preparation Guidelines and must be followed exactly.

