#### 264-Week Optional Ocrelizumab Extension

At Week 24, patients who have completed the 24–week period will be offered to continue ocrelizumab treatment in an optional treatment extension period with the dose initially assigned to them until the appropriate dosing regimen for the subsequent

#### Ocrelizumab—F. Hoffmann-La Roche Ltd 37/Protocol WA39085, Version 10

Phase III study in children and adolescents is selected by the IMC. At that time, patients will be assigned to this selected dosing regimen.

Should a subsequent dose be higher than the dose in the initial treatment regimen, that dose must be administered as two infusions of half the dose 14 days apart to mitigate the risk and severity of IRRs.

A re–evaluation of the benefit-risk of continuing study treatment by the treating investigator must be performed for each patient at the end of the first 24 weeks and prior to any further dosing, and therapy extension will only be granted to those patients where the benefit-risk is considered to be favorable.

The investigator should discuss the benefits and risks of continuing study treatment with the parents/legal guardian and patient in advance and prior to any further dosing.

For patients continuing the study, the second dose of ocrelizumab will be administered if all re-treatment criteria are met (Section 4.3.6).

See Figure 1 for the study schema. A schedule of activities is provided in Appendix 1.

IMC = Internal Monitoring Committee; OOE = Optional Ocrelizumab Extension.

- a Screening for the study may be extended but cannot exceed 10 weeks for relevant clinical, administrative, or operational reasons.
- b Eligible patients will be allocated into one of two treatment groups depending on their body weight at screening. The first dose of ocrelizumab for the 24-week period must be administered as two infusions of half the dose 14 days apart. Patients who receive a partial or complete dose of ocrelizumab and discontinue from the 24-week period will enter the safety follow-up period (at least *104* weeks).
- At Week 24, patients will have the opportunity to continue with ocrelizumab treatment by entering a 264–week optional ocrelizumab extension period. For patients continuing the extension, subsequent doses of ocrelizumab will be administered if all re-treatment criteria are met.

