## 3.1.1.3 264-Week Optional Ocrelizumab Extension

At Week 24, patients continuing with ocrelizumab treatment by entering a 264–week optional ocrelizumab extension (OOE) period will receive subsequent doses if re–treatment criteria are met (see Section 4.3.6).

A re–evaluation of the benefit-risk of continuing study treatment by the treating investigator must be performed for each patient at the end of the first 24 weeks and prior to any further dosing, and therapy extension will only be granted to those patients where the benefit-risk is considered to be favorable.

The treating investigator should discuss the benefits and risks of continuing study treatment with the parents/legal guardian and patient in advance and prior to any further dosing.

During the OOE period, patients will be evaluated for prespecified conditions and laboratory abnormalities as per the schedule of activities (see Appendix 1). The treating investigator must ensure patients meet criteria for re-treatment with ocrelizumab, as defined under Section 4.3.6, before each subsequent infusion.

Patients will continue in the OOE period with the dosing regimen initially assigned until the preferred and final pediatric dosing regimen is selected by the IMC. In a situation where a subsequent dose is higher than the initial treatment regimen, that dose must be administered as two infusions of half the dose 14 days apart to mitigate the risk and severity of IRRs.

The OOE period will last 264 weeks, and may be extended until the patient turns 18 years old (or as required per local regulation) or until commercial ocrelizumab is approved for children and available in the country for these patients, whichever occurs first. Initiation of an alternative treatment for MS may be considered by the investigator in which case the patient will enter the SFU period.

Patients completing the 264–week OOE period or patients who discontinue treatment prematurely will enter the *104*–week SFU period.

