- a The screening period may be extended but cannot exceed 10 weeks for relevant clinical, administrative, or operational reasons. Note: For the patient's convenience, the optional mobile nursing professional can be requested to collect blood samples and ship them directly to the central laboratory if any laboratory tests have to be repeated.
- b In this study, patients will be offered the possibility to continue ocrelizumab treatment in an optional treatment extension period with the dose (e.g., 300 mg or 600 mg) initially assigned to them until the appropriate dose for the subsequent Phase III study in children/adolescents is selected by the IMC (see Section 3.1.1.3). At that time, patients will be assigned to this selected dose level. In a situation where a subsequent dose of ocrelizumab is higher than the initial dose, that dose must be administered as two infusions of half the dose 14 days apart to mitigate the risk and severity of IRRs. In this case, the second infusion will take place as an optional infusion visit for split dose. For patients continuing the study, the second dose of ocrelizumab will be administered if all re-treatment criteria are met (footnote g). It is recommended that the treating investigator discuss with the parents/legal guardian and patient the benefits and risks of continuing study treatment with ocrelizumab, including treatment options, in advance and prior to any further dosing in order to schedule subsequent visits, accordingly, see footnotes d, e, and f.

- c **Optional MN visits**: At applicable sites, for patient convenience, all assessments at visits marked with (MN) may be performed by an MN professional at the patient's home or another suitable location instead of the clinical site (see Section 4.5.3.5). If during a visit the MN professional identifies any change in patient's health status (e.g., new or worsening neurologic symptoms or any other situation that may warrant an unscheduled site visit), the MN professional will contact the site immediately to report and discuss the findings. If required, an unscheduled visit will be scheduled as soon as possible with the site (i.e., within 7 days of symptom onset if possible). At sites where MN visits are not applicable, visits will take place at the clinical site.

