(see Section 3.1.1.3). At that time, patients will be assigned to this selected dose level. In a situation where a subsequent dose of ocrelizumab is higher than the initial dose, that dose must be administered as two infusions of half the dose 14 days apart to mitigate the risk and severity of IRRs. In this case, the second infusion will take place as an optional infusion visit for split dose. For patients continuing the study, the second dose of ocrelizumab will be administered if all re-treatment criteria are met (footnote c). It is recommended that the treating investigator discuss with the parents/legal guardian and patient the benefits and risks of continuing study treatment with ocrelizumab, including treatment options, in advance and prior to any further dosing in order to schedule subsequent visits. The OOE period will last 264 weeks, and may be extended until the patient turns 18 years old (or as required per local regulation) or until commercial ocrelizumab is approved for children and available in the country for these patients, whichever occurs first. Initiation of an alternative treatment for MS may be considered by the investigator in which case the patient will enter the SFU period.

- b **Optional MN visits**: At applicable sites, for patient convenience, all assessments at visits marked with (MN) may be performed by an MN professional at the patient's home or another suitable location instead of the clinical site (see Section 4.5.3.5). If during a visit the MN professional identifies any change in patient's health status (e.g., new or worsening neurologic symptoms or any other situation that may warrant an unscheduled site visit), the MN professional will contact the site immediately to report and discuss the findings. If required, an unscheduled visit will be scheduled as soon as possible with the site (i.e., within 7 days of symptom onset if possible). At sites where MN visits are not applicable, visits will take place at the clinical site.

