e Administration of IV ocrelizumab: The first dose of ocrelizumab must be administered as two infusions of half the dose 14 days apart (e.g., 150 mg on Day 1 and 150 mg on Day 15 for the 300 mg ocrelizumab cohort). It is recommended to schedule the first infusion of ocrelizumab (Day 1 of Dose 1) in the morning to allow the patient to stay at the hospital (or infusion center) with medical supervision and monitoring as required, as long as possible (e.g., until 6 p.m. or 8 p.m. according to the hospital rules), with a minimum of 1 hour after completion of the infusion. Patients may be hospitalized for a 24-hour observation after completion of the infusion at the discretion of the treating investigator. It is also recommended to administer the second infusion (Day 15 of Dose 1) and subsequent infusions in the morning, as patients should remain under observation for at least 1 hour after the completion of the infusion and up to 24 hours at the treating investigator's discretion.

For patients continuing in the optional ocrelizumab extension period (footnote a), subsequent doses will be administered as single infusions (e.g., 300 mg for the 300-mg ocrelizumab cohort). However, whenever the subsequent dose is higher than the previous dose, it should be administered as two infusions of half the dose 14 days apart. In this case, the second infusion will take place as an optional infusion visit for split dose. Prior to subsequent infusion of ocrelizumab, the treating investigator must review the clinical and laboratory re-treatment criteria (footnote c). Patients and their parents/legal guardian will be advised that an IRR can occur until 24 hours after completion of each infusion. A telephone interview will be conducted by site personnel within 24 ( $\pm$  4) hours after completion of each infusion (footnote h).

- f Unscheduled site or MN visit: Assessments performed at unscheduled (non-dosing) visits will depend on the clinical needs of the patient. All patients with new neurological symptoms suggestive of relapse should have EDSS performed within 7 days of the onset of the relapse. Other tests/assessments may be done as appropriate.
- g Withdrawal from treatment visit only takes place if patient discontinues prematurely from treatment (i.e., before Week 288) (see Section 4.5.3.6).

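### The trigger for giving a raised dose as two half-dose infusions is stated in two incompatible ways: higher than the initial dose in some places, higher than the previous dose in others

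*Combined protocol and SAP*

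**What the plan says.** Doses in the optional extension are single infusions every 24 weeks by default. A raised dose is an exception, and the protocol states its trigger in two forms.

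**Compared with the initial dose or regimen**
- Section 4.3.2.3: "where the subsequent dose is higher than the dose in the initial treatment regimen, that subsequent dose will be administered as two infusions".
- Section 3.1.1, under the extension heading: "Should a subsequent dose be higher than the dose in the initial treatment regimen, that dose must be administered as two infusions".
- Section 3.1.1.3, with the same wording in the Figure 1 note: "In a situation where a subsequent dose is higher than the initial treatment regimen, that dose must be administered as two infusions".
- Appendix 1, Table 1 footnote b and Tables 2a and 2b footnote a: "higher than the initial dose, that dose must be administered as two infusions of half the dose 14 days apart".

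**Compared with the previous dose**
- Appendix 1, the footnotes of Tables 1, 2a and 2b on IV administration of ocrelizumab (footnote e in Tables 2a and 2b): "whenever the subsequent dose is higher than the previous dose, it should be administered as two infusions of half the dose 14 days apart".

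Two further statements make the difference matter. Section 4.3.2.3 says that Cohort 1 patients who reach a stable weight of at least 40 kg "will be automatically switched to the appropriate dose for patients with body weight" of that range, and Section 3.1.1 says that 600 mg has now been determined as the dose for patients of 40 kg or more. Cohort 1 starts at 300 mg.

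**The concern.** The two triggers agree on the first raised dose and part company on every dose after it. Once a child has moved from 300 to 600 mg, each 600 mg dose is above the initial 300 mg, but only the first is above the dose before it. Each treatment-period schedule in Appendix 1 carries both triggers, so a site cannot settle the matter from the table alone.

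The situation is foreseeable. Cohort 1 enrols children from 10 years of age weighing 25 to under 40 kg, and treatment can last 288 weeks, so some may well grow past the threshold.

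At stake is what children receive. Every extra infusion brings mandatory methylprednisolone and antihistamine (Section 4.3.3), a separate split-dose visit and a telephone interview at 24 hours. Two sites could each follow the protocol and treat identical patients differently.

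Infusion-reaction data would be affected too. Section 6.6 reports adverse events per 100 patient-years, and an additional infusion adds an occasion for a reaction without adding person-time.

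**Working it through.** The plan gives no figure to reproduce here, so the check is a comparison of texts followed by a count.

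**Step 1. Is either rule limited or ranked?** No statement using *initial* restricts the split to the first raised dose, and no section says that one statement prevails. Table 1 footnote f also says *initial*, but it concerns only the second dose, for which initial and previous dose are the same.

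**Step 2. Inputs for the count**
- Extension dosing visits at Weeks 24, 48, ..., 264 (Appendix 1, Tables 1, 2a and 2b): (264 − 24)/24 + 1 = 11 doses.
- Dose before the switch 300 mg, and from the switch 600 mg (Sections 3.1.1 and 4.3.2.3).
- Assumptions: no dose delayed by more than 4 weeks, and no further dose change.

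**Step 3. Formula.** For a switch at Week *s*, the number of 600 mg doses is n = (264 − s)/24 + 1.
- *Initial* rule: all n doses are split, giving 2n infusions.
- *Previous* rule: one dose is split, giving n + 1 infusions.
- Difference: 2n − (n + 1) = n − 1 = (264 − s)/24.

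**Step 4. Results**

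| Switch at Week | 600 mg doses (n) | Infusions, *initial* rule | Infusions, *previous* rule | Difference |
|---|---|---|---|---|
| 24 | 11 | 22 | 12 | 10 |
| 48 | 10 | 20 | 11 | 9 |
| 144 | 6 | 12 | 7 | 5 |
| 240 | 2 | 4 | 3 | 1 |
| 264 | 1 | 2 | 2 | 0 |

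Premedication is mandatory before each infusion, so the last column also counts extra premedications.

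**Step 5. How much reaches the PK data?** Section 4.5.19.6 and Table 2a end extension PK sampling at Week 96. Take the Week 48 switch:
- The Week 72 trough follows the Week 48 dose, which both rules split, so the rules do not alter it.
- The Week 96 trough follows the Week 72 dose, which is split under one rule and single under the other. It is the only scheduled extension trough that can differ.

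For a switch at Week 24, the Week 72 and Week 96 troughs can differ. For a switch at Week 72 or later, none can. Table 2a marks no PK sample at the optional split-dose visit.

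**The case against.** The best defence is that the authors meant only the step-up dose. The wording is singular, the stated purpose is to reduce infusion-related reactions, the text around *initial* mostly describes the change to the regimen chosen by the monitoring committee, and single infusions are the default. That is a plausible account of intent, but no section says it, and sites follow the text. Section 4.3.2.3 also refers to separate Dose Preparation Guidelines. They are not in these documents, so whether sites would diverge in practice is unknown.

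Three stronger readings are tempting, and the documents do not support them.

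- *The body text says one thing and the footnotes another.* Footnotes in all three tables also use *initial*. Only the administration footnotes use *previous*.
- *Every patient whose dose is raised is affected.* The rules coincide for a switch at Week 264, and any dose delayed by more than 4 weeks is split under either (Section 4.3.5).
- *The PK summaries are seriously compromised.* With the adult parameters in Section 1.2.2 (clearance 0.17 L/day, central and peripheral volumes 2.78 and 2.68 L, intercompartmental clearance 0.294 L/day), constant clearance, bolus input and steady state, splitting 600 mg raises the 24-week trough from 0.89 to 1.09 mg/L (ratio 1.23) and lowers the peak from 217 to 138 mg/L (ratio 0.64). The trough change is only 0.20 mg/L and would appear in few samples (step 5), and the split-dose peak would not be sampled. AUC is model-based, and Dose 1 in the dose exploration period is split for everyone. Split and single administration are mixed in any case, because first and delayed doses are split.

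One qualification remains. Section 4.5.19.6 describes extension samples as predose, whereas Table 2a footnote cc adds a sample after the infusion. If that sample is taken, it would follow a half dose under one rule and a full dose under the other at Weeks 72 and 96 in the Week 48 example.

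**Conclusion.** The point holds as a contradiction in current operative text, with a real but bounded effect. A patient switched from 300 to 600 mg would receive 0 to 10 more infusions, with premedication, under one trigger than under the other, depending on the switch visit. The count rests on the literal wording, the planned visits at Weeks 24 to 264, no delays beyond 4 weeks and no further dose change. The protocol does not say how many patients will switch or when. The weight-triggered switch concerns Cohort 1, planned at 6 patients.

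The main consequence is inconsistent treatment and infusion-reaction counts. The effect on PK is minor. All analyses are descriptive (Section 6), so no sample size, test or other statistical figure changes. Which trigger is right is a clinical matter and is not judged here.

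**What to change.** Reconcile Sections 3.1.1, 3.1.1.3 and 4.3.2.3, the Figure 1 note and the footnotes of Appendix 1 Tables 1, 2a and 2b so that one trigger applies throughout. State explicitly whether it covers only the first raised dose or every dose at the higher level. The sponsor should choose the trigger on clinical grounds and check the Dose Preparation Guidelines against it. The cost is wording in an amendment.

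A variable marking split or single administration in the PK dataset would be useful because the modes mix anyway, but it is optional and not needed for this fix.
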